1. INTRODUCTION

1.1 Literature Review

Colorectal cancer is the second leading cause of cancer-related deaths worldwide. It is estimated that 10% of cancer mortality is attributed to malignant neoplasms of the colon and rectum [1]. More specifically, in the United States alone, 53,200 colorectal cancer deaths were reported [2].

The current treatment of choice for locally advanced rectal cancer (Stage II/ III) is the combination of neoadjuvant chemoradiation followed by radical surgical resection based on the principles of total mesorectal excision (TME) after a 8-12 weeks period [3]. Therapy is usually completed with the administration of adjuvant chemotherapy based on oxaliplatin and fluoropyrimidines. This combined approach allowed the reduction of local recurrence at levels around 5%. Despite the impressive results in local control, the same was not confirmed for the long-term, overall survival. Possible explanations to that are: a) the compliance and completion of the treatment schemes during the postoperative period were low and b) there was a delay in the administration of adjuvant chemotherapy; both could lead to subclinical metastatic disease progression [4].

On the basis of achieving both goals, (i.e., local control through neoadjuvant radiotherapy and metastatic disease control through systemic chemotherapy) the administration of the two therapies in the preoperative period was proposed, in the form of combined or total neoadjuvant therapy [1, 5–8].

Additional theoretical benefits of total neoadjuvant therapy are faster defunctioning stoma reversal, as well as the possibility of a more accurate evaluation of the tumor biological behavior, thus enabling a safer staging for patients who would be candidates for a watch and wait protocol [1–3, 5–12]. Furthermore, for patients who will eventually undergo surgery, total neoadjuvant therapy could probably increase R0 resection and sphincter-preservation rates [3, 5, 8– 10, 12].

However, many researchers question the safety and efficacy of total neoadjuvant therapy [7, 13]. First, the administration of neoadjuvant chemotherapy significantly increases the risk of

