severe toxicity from cytotoxic agents [14]. At the same time, according to the results of one of the largest prospective randomized trials, the addition of neoadjuvant chemotherapy into the treatment algorithm did not offer any advantage in the pathological response, 5-year overall and disease-free survival rates [15]. Finally, there is considerable heterogeneity in the current literature, most likely reflecting the different schemes used in different trials regarding the radiotherapy regimen, the chemotherapy regimen as well as the sequence of each one in each protocol [16].

We believe it is difficult to interpret any differences in results when multiple parameters have been changed in a comparative trial [17]. For this reason, when testing our current standard neoadjuvant protocol to the new trend of total neoadjuvant therapy we decided to keep the same scheme and timing for the experimental group also, and the only parameter which is different is the use of the classic chemotherapy scheme during the waiting period following chemoradiation and before surgery [18].

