3.4 Study Arms

In this study there will be two arms [5, 10]. Patients that are randomized in the first arm will receive neoadjuvant chemoradiotherapy and consolidation chemotherapy and then undergo surgical resection of the tumor. In the second arm, patients will receive the standard long-course neoadjuvant chemoradiotherapy regimen and then undergo tumor resection. The treatment will be completed with adjuvant chemotherapy. In both groups, surgery will follow the principles of total mesorectal excision (TME).

The control group will receive the standard 5-week neoadjuvant chemoradiotherapy regimen. Six weeks after completion the patient will be re-staged with rectal MRI and depending on the response will be operated (TME): immediately in case of non-response (mrTRG 5) or after an additional 6-week delay (overall 12 weeks after the end of chemoradiotherapy) in case of partial response (mrTRG 2-4). Adjuvant chemotherapy will be, also, administered.

The experimental group will receive the standard 5-week neoadjuvant chemoradiotherapy (CRT). Thereafter, all patients will commence consolidation chemotherapy. At the 6th week after the end of CRT, patients will undergo MRI re-staging: In case of non-response (mrTRG 5) they will be submitted immediately to surgery, and, subsequently, excluded from the trial. In case of response (mrTRG 2-4) they will receive consolidation chemotherapy for the whole waiting period between the end of CRT and surgery - 12 weeks.

The following interventions will be introduced:

Neoadjuvant Chemoradiotherapy. 5-week neoadjuvant radiotherapy regimen (28 x 1.8 Gy) combined with Capecitabine (bid 800 mg/m², twice daily, on days 1-33-38)

Consolidation Chemotherapy. CAPOX (Capecitabine bid 1000 mg/m² and Oxaliplatin 130 mg/m², day 1, every 3 weeks) or alternatively FOLFOX

Adjuvant Chemotherapy. 8 cycles of CAPOX (Capecitabine bid 1000 mg/m², twice daily, day 1-14, every 3 weeks and Oxaliplatin 130 mg/m², day 1, every 3 weeks) or alternatively, 12 cycles of folinate, fluorouracil and oxaliplatin (FOLFOX)

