3.8 Secondary endpoints

Secondary endpoints of the present study are:

Complete Pathological Response. Occurrence of Complete Pathological Response. If such an episode occurs, then it will be defined as=1 'YES' If such an episode does not occur, then it will be defined as=0 'NO'. [Time Frame: 1 month postoperatively]

Postoperative Complications. Occurrence of postoperative complications based on the Clavien Dindo Classification [20]. If such an episode occurs, then it will be defined as=1 'YES' If such an episode does not occur, then it will be defined as=0 'NO'. [Time Frame: 1 month postoperatively]

Length of Hospital Stay. Postoperative time that the patient can be safely discharged. Measurement unit: days. The patient will be discharged, when it is ensured that is medically safe

to be released. In particular, as the exit time of the patient, will be regarded the time that the patient will fulfil the Clinical Discharge Criteria. [Time Frame: Maximum time frame 39 days postoperatively]

Readmission. Occurrence of postoperative readmission. If such an episode occurs, then it will be defined as=1 'YES' If such an episode does not occur, then it will be defined as=0 'NO'. [Time Frame: 1 month postoperatively]

Negative Resection Margin. Occurrence of Negative Resection Margin. If such an episode occurs, then it will be defined as=1 'YES' If such an episode does not occur, then it will be defined as=0 'NO'. [Time Frame: 1 month postoperatively]

Overall Survival. Occurrence of Overall Survival. If such an episode occurs, then it will be defined as=1 'YES' If such an episode does not occur, then it will be defined as=0 'NO'. [Time Frame: 3 years postoperatively]

Chemotherapy Toxicity. Occurrence of Chemotherapy Toxicity. If such an episode occurs, then it will be defined as=1 'YES' If such an episode does not occur, then it will be defined as=0 'NO'. [Time Frame: 3 years postoperatively]

Local Recurrence. Occurrence of Local Recurrence. If such an episode occurs, then it will be defined as=1 'YES' If such an episode does not occur, then it will be defined as=0 'NO'. [Time Frame: 3 years postoperatively]

Treatment Compliance. Occurrence of Treatment Compliance. If such an episode occurs, then it will be defined as=1 'YES' If such an episode does not occur, then it will be defined as=0 'NO'. [Time Frame: 3 years postoperatively]

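### Chemotherapy Toxicity, the trial's only toxicity measure, is a single yes/no flag with no severity threshold or treatment phase, so a difference in severe toxicity between arms cannot be recovered from it.

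*Protocol*

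**What the plan says.** Protocol section 3.8 defines the endpoint as "Chemotherapy Toxicity. Occurrence of Chemotherapy Toxicity. If such an episode occurs, then it will be defined as=1 'YES", with 0 if no episode occurs. The time frame is three years after the operation. No toxicity scale, grade cut-off, drug or phase is attached to it there or anywhere else in the Protocol.

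Section 1.1 opens its account of the doubts about total neoadjuvant therapy with this statement, which runs across a page break: "First, the administration of neoadjuvant chemotherapy significantly increases the risk of" "severe toxicity from cytotoxic agents [14".

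Section 3.4 sets out the exposure. Both arms receive capecitabine with radiotherapy. For the experimental arm: "The experimental group will receive the standard 5-week neoadjuvant chemoradiotherapy (CRT). Thereafter, all patients will commence consolidation chemotherapy". Responders at the MRI re-staging continue: "they will receive consolidation chemotherapy for the whole waiting period between the end of CRT and surgery - 12 weeks". For the control arm, after surgery: "Adjuvant chemotherapy will be, also, administered", given as "8 cycles of CAPOX" or, alternatively, 12 cycles of FOLFOX. Read with the objective in section 2.1, adjuvant treatment belongs to the control arm.

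By contrast, the surgical harm endpoint in section 3.8 does name a scale: "Occurrence of postoperative complications based on the Clavien Dindo Classification [20".

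**The concern.** The harm that the Protocol itself attributes to neoadjuvant chemotherapy is a matter of severity. The endpoint that should address it carries no severity. The other harm-related endpoints (postoperative complications, readmission) and treatment compliance measure different things, so nothing else in section 3.8 fills the gap.

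The flag also pools phases that play different roles in the comparison: chemoradiotherapy, common to both arms; consolidation, experimental arm only; and adjuvant treatment, control arm only. At stake is whether the trial can say anything about severe toxicity with and without consolidation. This is a secondary endpoint, and the primary endpoint and sample size are not affected.

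**Working it through.** **Inputs.** Yes/no coding and time frame: section 3.8. Treatment phases: section 3.4. Group size of 42: section 3.9. The Protocol states no toxicity rate and no toxicity calculation, so there is no plan figure to reproduce. Every rate below is an assumption for illustration.

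**Step 1: what the coding loses.** Let f be the proportion flagged in an arm and s the proportion with severe toxicity. Every severe case is flagged, so s can lie anywhere from 0 to f.

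- With flagged proportions f_C (control) and f_E (experimental), the difference s_E - s_C can lie anywhere from -f_C to +f_E.
- If both arms show f = 50%, the flag difference is 0 and the severe difference could be anything from -50 to +50 points. At f = 80% it could be anything from -80 to +80 points.
- Example at f = 80% in both arms. Control: 10% severe and 80 - 10 = 70% mild only. Experimental: 30% severe and 80 - 30 = 50% mild only. Severe cases are 0.10 x 42 = 4.2 against 0.30 x 42 = 12.6, yet the coded endpoint is identical.

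This step needs no assumption about the size of the rates. It follows from giving mild and severe events the same value.

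**Step 2: the time window.** Two readings are possible.

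- *The window starts at surgery (literal).* Chemoradiotherapy and consolidation toxicity fall outside it, and the control arm's adjuvant toxicity falls inside. The flag would then tend to count against control, and severity is still lost.
- *Three years after surgery is only the end date.* All phases count, severity is lost, and step 3 also applies.

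Step 1 holds under both readings.

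**Step 3: the shared phase, only if preoperative events count.** Let p be the share already coded 1 by chemoradiotherapy, equal in expectation in the two arms because they are randomised. Each arm's final proportion lies between p and 1, so the arms can differ by at most 1 - p.

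- p = 50%: at most 1 - 0.50 = 50 points.
- p = 80%: at most 1 - 0.80 = 20 points.

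These are upper limits and do not predict the observed difference.

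**Step 4: unequal exposure after the shared phase.** If the 12-week wait is filled with three-weekly CAPOX, consolidation is about 12 / 3 = 4 cycles, against 8 adjuvant cycles in control. A flag without phase cannot separate these from each other or from chemoradiotherapy.

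**Step 5: what 42 per arm can support.** Two-sided 5%, normal approximation: power = Φ{[|p1 - p2| - 1.96 √(2p̄(1 - p̄)/n)] / √([p1(1 - p1) + p2(1 - p2)]/n)}, where p̄ is the mean of p1 and p2.

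| Assumed contrast | Power at n = 42 |
|---|---|
| Any toxicity 85% vs 95% | 0.33 |
| Any toxicity 90% vs 95% | 0.14 |
| Any toxicity 95% vs 98% | 0.11 |
| Severe 20% vs 30% | 0.18 |
| Severe 15% vs 35% | 0.56 |
| Severe 20% vs 40% | 0.52 |
| Severe 20% vs 50% | 0.83 |

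The rows for any toxicity and for severe toxicity are separate assumptions and are not paired. They show that a contrast close to the ceiling has little power. They also show that a graded endpoint estimates the right quantity but would detect only large differences.

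**The case against.** The strongest objection is that the Protocol never says any grade. It leaves the word episode undefined, and a scale and threshold could be set in a SAP or case report form that is not shown. Most endpoints in section 3.8 follow the same yes/no template, and even complications, where a classification is cited, are coded yes/no. So the template does not show that grades will go uncollected. Part of this stands: one cannot conclude that severity will never be recorded. But the Protocol has itself fixed the variable and its coding, and the plain reading of occurrence without a threshold is that any toxicity counts. An analysis that follows the text compares two such proportions.

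A reader might also infer that the flag will sit near 100% in both arms and so lead to a false conclusion of equal safety. The documents do not support that. With 80% flagged in chemoradiotherapy and 80% in later chemotherapy, independently, the flag is 1 - 0.2 x 0.2 = 96%. Those rates are assumed, and making them equal in both arms guarantees a zero difference. The argument also needs chemoradiotherapy toxicity to count. Under the literal window it does not, and the flag would then tend to differ, against control.

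Two further inferences go too far. Section 1.1 lists severe toxicity first among the objections but does not call it the main risk. Section 3.16 says that patient data go into charts and a database, and does not say that toxicity grades are among them.

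**Conclusion.** The concern holds for the coding. As section 3.8 stands, the trial's only toxicity endpoint gives mild and life-threatening events the same value, so it cannot show whether severe toxicity differs between arms. That conclusion rests on reading occurrence as having no severity threshold, since none is stated. It does not depend on any assumed rate or on which time window is meant.

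The masking by the shared chemoradiotherapy is conditional. It applies only if preoperative events are counted, and its size depends on any-grade rates that the Protocol does not give. The limit on the difference is 1 - p, for example 50 points at p = 50% and 20 points at p = 80%. Neither a ceiling effect nor a false finding of safety is established. The change is worth making because this is the sole toxicity measure, although it is a secondary endpoint.

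**What to change.** In section 3.8:

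- Name a standard toxicity grading scale and record the worst grade per patient.
- Make the safety endpoint the proportion of patients with at least one event of grade 3 or higher.
- Report it overall and by phase: chemoradiotherapy, consolidation, adjuvant.
- Start the window at the first dose of study treatment. Without this, by-phase reporting would miss both preoperative phases under the literal time frame.
- Keep any/none as a descriptive summary.

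The cost is endpoint wording, a few graded fields in the database and slightly more data entry. Grades should be collected prospectively, because the Protocol does not say that they are recorded and they may be hard to reconstruct later. At 42 per group the result is best presented as an estimate with a confidence interval, since only large differences in severe toxicity would be detected reliably.

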3.9 Calculation of the sample size

The sample size calculation was based on the primary endpoint. According to the literature, the disease-free survival Hazard Ratio between standard practice and combined neoadjuvant therapy is 0.23 [21]. Therefore, for a prospective randomized study with alpha: 5%, power: 90% and dropout

rate: 15%, the estimated number of patients in each group is 42. A total of 84 patients will be required.

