3.7 Primary endpoint

Disease Free Survival. Occurrence of Disease Free Survival. If such an episode occurs, then it will be defined as=1 'YES' If such an episode does not occur, then it will be defined as=0 'NO'. [Time Frame: 3 years postoperatively]

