3.13 Monitoring

Following hospital discharge, the patient will be called for reassessment at one month after the operation. Patients will be included in the standard monitoring protocol (CT, MRI, cancer markers), unless otherwise required. At the same time, the pathological assessment of the specimen will be recorded. In addition, at 3 and 5 years postoperatively, overall, disease-free survival and recurrence rates will be recorded.

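### Section 3.9 sizes the trial on a DFS hazard ratio, section 3.7 fixes DFS as a yes/no status at 3 years, and the control rate that would link the two is not stated

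*Protocol*

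**What the plan says.** Protocol section 3.9 opens with "The sample size calculation was based on the primary endpoint". It then reports from the literature that "the disease-free survival Hazard Ratio between standard practice and combined neoadjuvant therapy is 0.23 [21", and carries this into the calculation. The design settings are given as "for a prospective randomized study with alpha: 5%, power: 90% and dropout", and the allowance for losses and the resulting size as "rate: 15%, the estimated number of patients in each group is 42. A total of 84 patients will be required". It gives no control-arm DFS and no number of events.

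Section 3.7 defines the endpoint in question: "Occurrence of Disease Free Survival. If such an episode occurs, then it will be defined as=1 'YES" and "If such an episode does not occur, then it will be defined as=0 'NO'. [Time Frame: 3 years postoperatively". It gives no event date, no list of qualifying events and no censoring rule. Its only time reference is to surgery.

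Section 3.13 plans routine surveillance: "Patients will be included in the standard monitoring protocol (CT, MRI, cancer markers), unless otherwise required". For the outcome itself it says that "at 3 and 5 years postoperatively, overall, disease-free survival and recurrence rates will be recorded". It speaks of rates and does not mention dates of events.

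**The concern.** A hazard ratio compares event rates over time. It is estimated from event times, with patients who leave early censored. A status read once at 3 years yields two proportions. Section 3.9 says that it sizes the endpoint of section 3.7, yet the effect measure in one is not what the other estimates.

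Two further problems come from the same definition.

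- **Meaning of the code.** The episode is named as disease-free survival itself. Literally, 1 is a good outcome. By analogy with the other endpoints coded in this way, such as local recurrence, a reader could take 1 as a DFS event.
- **Patients lost early.** Section 3.9 expects 15% dropout. Inflating the sample replaces their number but does not classify them. A time-to-event endpoint uses each such patient up to the last assessment; a yes/no status has no category for them.

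At stake are what the primary result of an 84-patient trial will estimate, and whether a reader can judge the claim of 90% power.

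**Working it through.** **Inputs from the protocol.** HR 0.23, read as experimental over control; alpha 5%, power 90%, dropout 15%, 42 per group (section 3.9); 1:1 allocation (section 3.10); yes/no status at 3 years (section 3.7).

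**Assumptions, because the protocol gives no figure.** Control 3-year DFS, written S, is scanned. Hazards are proportional, so experimental 3-year DFS is S^0.23. Event times are exponential, 15% are lost by year 3 independently of prognosis, and the test is two-sided unless noted.

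**Step 1. Can 42 be reproduced from a hazard ratio?**

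- Schoenfeld: events = 4 × (1.960 + 1.282)² / (ln 0.23)² = 4 × 10.51 / 2.16 = 19.5, so 20.
- Freedman: events = (1.23 / 0.77)² × 10.51 = 26.8, so 27.
- To turn events into patients, S is needed. At S = 0.55, S^0.23 = 0.872, and the mean event probability is (0.450 + 0.128) / 2 = 0.289. Then 20 / 0.289 = 69.2 patients, or 35 per group, and 35 / 0.85 = 41.2, so **42**.
- Freedman reaches 42 at S of about 40–41%. One-sided, Schoenfeld (16 events) reaches it at about 64% and Freedman (22 events) at about 51%.

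**Step 2. Can 42 be reproduced from two proportions?** At S = 0.50, S^0.23 = 0.853, with mean proportion 0.676:

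n = [1.960 × √(2 × 0.676 × 0.324) + 1.282 × √(0.500 × 0.500 + 0.853 × 0.147)]² / (0.853 − 0.500)² = 34.9, so 35; and 35 / 0.85 = 41.2, so **42**.

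Both kinds of comparison therefore give 42, each with a different control rate that the protocol does not state. The stated inputs alone do not determine it.

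**Step 3. Power of the planned size.** For the yes/no comparison, 42 × 0.85 = 35.7, so 36 per arm, with power by exact binomial enumeration of the uncorrected chi-square test. For the log-rank test, 42 per arm were simulated with losses censored and follow-up ending at 3 years.

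| Assumed control 3-year DFS | Yes/no, 36 per arm | Log-rank, 42 per arm |
|---|---|---|
| 50% | 92% | 93% |
| 52% | 90% | 92% |
| 55% | 88% | 90% |
| 65% | 77% | 80% |
| 70% | 70% | 73% |
| 75% | 62% | 64% |

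The 90% thus holds up to a control DFS of about 52% (yes/no) or 55% (log-rank). With a one-sided test the limits are about 59% and 63%.

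**Step 4. What does the form of the endpoint cost?** At control DFS 65/70/75%:

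| Analysis | Power |
|---|---|
| Log-rank, losses censored | 80/73/64% |
| Yes/no, 36 per arm | 77/70/62% |
| Yes/no, known status only | 80/73/64% |
| Yes/no, dropouts counted as event-free | 80/74/66% |

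The log-rank test gains 3 to 4 points at most, and nothing over the last two analyses.

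The estimate also depends on the handling of losses. At a true control DFS of 70%, the share event-free and still followed is 0.70 × 0.85 = 0.595. With cumulative hazards of 0.357 for events and 0.163 for loss, the share with an event before loss is 0.357 / 0.520 × 0.405 = 0.278. The yes/no proportion then reads 1 − 0.278 = 72.2% with dropouts as event-free, or 0.595 / (0.595 + 0.278) = 68.1% on known status only. Kaplan-Meier targets 70%.

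**The case against.** The strongest reply is that the gap is one of wording. A hazard ratio can be converted to 3-year proportions, and Step 2 does so and lands on 42. A complementary log-log model could recover a hazard ratio from binary data. The same 1/0 template is used for every endpoint in sections 3.7 and 3.8 except length of stay, and a 1/0 indicator within a time window is an ordinary component of survival data. Rules for missing outcomes, the test and its sidedness are commonly left to a SAP, and none is at hand.

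Much of this stands. Silence on test, sidedness and missing-data rules is not counted here as a fault. What does not fall away is that the protocol itself fixes the endpoint as a status, says that the sizing rests on it, and gives neither the conversion nor the control rate that would connect the two. No complementary log-log model is specified.

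A reader might go further and infer that dropouts will be coded as failures. Under that coding, power at control DFS 65/70/75% would be 57/47/37%, which is 23 to 27 points below the log-rank test. With an assumed loss of 20% in control and 10% in the experimental arm, and no treatment effect, false positives would be about 11% at a DFS of 70%. The documents support neither step. Section 3.7 assigns 0 when the episode does not occur and says nothing of unknown status, and no unequal loss is stated. These figures are hypothetical.

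**Conclusion.** The concern holds in a limited form. Sections 3.7 and 3.9 do not fit together: the sizing uses a hazard ratio, while the endpoint as coded estimates none, is ambiguous in direction and has no place for the expected dropouts. This can be read from the text and needs no assumption.

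The numerical part is conditional. That 42 per group is wrong, or that the trial is underpowered, might be inferred from the 65–75% rows, but the documents give no control rate against which to judge. At 50–55% the stated 90% is met or nearly met under both analyses; above that it is not. The result rests on proportional hazards, exponential times and 15% independent loss by year 3, and section 3.9 does not define dropout that closely.

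Nor do lost patients generally weigh as much as the events. Expected events against patients lost without an event are 25.3 against 10.4 at a control DFS of 50% (ratio 0.41), 17.3 against 11.2 at 65% (0.64) and 12.2 against 11.6 at 75% (0.95). Near parity appears only at the top of the assumed range.

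The endpoint should be corrected for coherence and clear interpretation. The gain in power is small.

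**What to change.** **Section 3.7.** Define DFS as the time from randomisation to the first DFS event, list the events that count, and censor patients without an event at their last disease assessment. Randomisation as origin also gives a value to patients who are never operated on. Compare the arms by log-rank test, give the Cox hazard ratio with its confidence interval, and report 3-year DFS by Kaplan-Meier.

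**Section 3.9.** State the control 3-year DFS and the required number of events behind 42 per group. If that control DFS is above about 55% (two-sided log-rank), restate the power that 84 patients give.

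**Section 3.13.** State that the date of the first event and the date of the last disease assessment are recorded, taken from the CT and MRI monitoring already planned.

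**Cost.** Rewording, and two dates per patient; no extra patients or visits if routine imaging dates are used. There are three drawbacks. The stated power may become less favourable. Censoring assumes that loss is unrelated to prognosis, so a sensitivity analysis is advisable. A hazard ratio from few events (about 12 to 17 at a control DFS of 65–75%) will be imprecise.
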